8.6 Safety

8.6.1 Adverse Events

8.6.1.1 Definition of Adverse Event

The definitions below follow International Conference on Harmonization (ICH) – Good Clinical Practice (GCP) (see also ICH Guideline for Clinical Safety Data Management: Definitions and Standards for Expedited Reporting).

Adverse Event (AE)

An AE is defined as any untoward medical occurrence in a subject administered a pharmaceutical product and which does not necessarily have a causal relationship with this treatment. An AE can therefore be any unfavorable and unintended sign (including an abnormal laboratory finding), symptom, or disease temporally associated with the use of a medicinal (investigational) product, whether or not considered related to the medicinal (investigational) product.

Any clinically significant change in a condition (worsening) from screening that results in a change in subject management will be considered an AE and will be recorded on the AE page of the CRF.

By definition for this study, all untoward medical occurrences beginning on the day of Visit 2 Baseline (Day 1) through the Follow-up Phone Call are to be reported as AEs. AEs continuing after study completion will be followed to normalization or stabilization. Additionally, untoward medical events occurring prior to the day of Tc 99m tilmanocept administration will be collected and added to the subject's medical history unless they are related to a study procedure, in which case the event will be recorded as an AE. SAEs will be reported from the time of consent through the end of participation.

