8.6.1.3 Assessments and Documentation of Adverse Events

Attention shall be paid to the occurrence of AEs for the duration of subject participation. Events occurring prior to Visit 2 (day of Tc 99m tilmanocept administration) will be recorded in the subject's medical history unless determined to be related to the study procedure. Untoward medical events beginning on Visit 2 (day of Tc 99m tilmanocept administration) through the completion of the Follow-up Phone Call will be reported as adverse events. Thus, subjects should be closely observed by the investigator both during and after the evaluation.

Any AE (observed, volunteered, or elicited) should be recorded in detail in the source documentation.

The following information is required:

- The **date and time of onset** of any AE.
- The duration (the entire duration of an event or symptom, calculated from date of onset to date of end, if not recorded directly).
- The seriousness of the AE will be assessed by the investigator. If the investigator deems that an AE qualifies as an SAE, a special form provided by the sponsor should be completed and the event must be immediately reported to the sponsor. A definition of SAEs is provided in [Section 8.6.1.5](#).
- The maximum intensity (mild, moderate, or severe).
- Whether drug treatment was administered for the event, any specific drug treatment must be documented.
- The relationship of the AE to the investigational product and to study conduct (for definitions, see above).

The **outcome** of the AE (resolved, resolved with sequelae, not resolved, unknown, death).

AEs will be coded according to an internationally recognized dictionary (Medical Dictionary for Regulatory Activities [MedDRA]).

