9.5.4 Analysis of Safety Variables

The number and percentage of subjects with ADRs will be tabulated by dose group and overall.

All AEs will be observed for each subject from the time of signing of informed consent until exit from the study. A treatment emergent adverse event (TEAE) is defined as an adverse event whose start date is on or after the Tc 99m tilmanocept injection date and time. If the injection date and time and/or the AE start date are missing, the AE will be considered treatment emergent.

Prior to analysis, all AEs will be coded using the MedDRA coding dictionary. Based on these coded terms, treatment emergent AEs will be summarized by dose group and overall as follows:

- by system organ class and preferred terms
- by system organ class and preferred terms and relation to study drug
- by system organ class and preferred terms and severity

Observed and change from baseline vital sign parameters, ECG parameters and hematology, clinical chemistry and urinalysis parameters will be summarized using descriptive statistics (mean, median, standard deviation, minimum, maximum and range) by dose group and overall.

Other safety analyses will be described in the SAP for the study.

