5.0 Analysis of Safety

Adverse Drug Reactions (ADRs) are defined as all noxious and unintended responses to a medicinal product related to any dose or dose regimen. The phrase 'responses to a medicinal product' means that a causal relationship between a medicinal product and an adverse event. The primary safety variable is the proportion of patients experiencing at least one ADR. The number and percentage of subjects with ADRs will be tabulated by dose group and overall. Other safety endpoints are noted below.

Analysis of Safety Endpoints

Attention shall be paid to the occurrence of adverse events (AEs) from the time of signing informed consent until exit from the study. Events occurring prior to Tc 99m tilmanocept administration will be recorded in the subject's medical history unless determined to be related to the study procedure. A treatment emergent adverse event (TEAE) is defined as an adverse event whose start date is on or after the first study drug administration date. If the study drug administration date and/or the AE start date are missing, the AE will be considered treatment emergent.

Prior to analysis, all AEs will be coded using the Medical Dictionary for Regulatory Activities (MedDRA). The MedDRA version used will be stated in the final validated tables. Based on these coded terms, AEs and TEAEs will be summarized by dose group and overall as follows:

- by system organ class and preferred terms;
- by system organ class and preferred terms and relation to study drug; and,
- by system organ class and preferred terms and severity.

In addition to the above endpoints, the following describes the analyses of the other safety data being collected for the study.

Vital Signs

Vital signs will include heart rate, blood pressure, respiration rate, and body temperature. Vital signs will be taken during screening, prior to study drug administration on Day 1 (and Day 7 [\pm 3] for Cohort 3), and within 30 minutes following study drug administration. For each vital sign, summary statistics

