Cohort	Subject No.	WHO Drug Preferred Term ^a / Verbatim Drug Name / Indication / ATC Level 1 Code / ATC Level 4 Code	Start Date	Stop Date	Route	Ongoing?
xxxxxx	xxxxxxx	xxxxxxxxxxxxxxxxxxxxxxxxxxxxxx xxxxxxxxxxxxxxxxxxxxxxxxxxxxxx xxxxxxxxxxxxxxxxxxxxxxxxxxxxxx xxxxxxxxxxxxxxxxxxxxxxxxxxxxxx xxxxxxxxxxxxxxxxxxxxxxxxxxxxxx	xxxxxx	xxxxxx	xxxxx	xxxxx
xxxxxx	xxxxxxx	xxxxxxxxxxxxxxxxxxxxxxxxxxxxxx xxxxxxxxxxxxxxxxxxxxxxxxxxxxxx xxxxxxxxxxxxxxxxxxxxxxxxxxxxxx xxxxxxxxxxxxxxxxxxxxxxxxxxxxxx xxxxxxxxxxxxxxxxxxxxxxxxxxxxxx	xxxxxx	xxxxxx	xxxxx	xxxxx

^a Concomitant medications coded with WHO Coding Dictionary xxxxxxxxx
Cohort 1 = 100µg/5mCi IV; Cohort 2 = 100µg/10mCi IV; Cohort 3 = 200µg/5mCi IV and SC.
STATKING Clinical Services (DD-MMM-YYYY)
Source Program: xxxxxxx.sas

Data Listing 8. Adverse Events Data Listing
 Navidea Biopharmaceuticals - Study No. NAV3-24
 Safety Population (N=xxxx)

Cohort	Subject No.	AE Start Date and Time/	Start Date and Time of most recent tilmanocept injection	MedDRA System Organ Class ^a / MedDRA Preferred Term/ CRF Verbatim Term	Treatment Emergent?	Adverse Drug Reaction (Y/N)	Severity	Relation to: Tc-99m tilmanocept/ Procedure	Serious	Outcome
		End Date and Time								
xxxxxx	xxxxxxxxxx	xxxxxxx	xxxxxxx	xxxxxxxxxxxxxxxxxxxx	xxx	xxx	xxxxxxxxxx	xxxxxxxxx/xxxxxxxxx	xxx	xxxxxxxxxx
		xxxxxxxx/	xxxxxxxx	xxxxxxxxxxxxxxxxxxxx						x
		xxxxxxxx		xxxxxxxxxxxxxxxxxxxx						
		xxxxxxxx		xxxxxxxxxxxxxxxxxxxx						
xxxxxx	xxxxxxxxxx	xxxxxxx	xxxxxxx	xxxxxxxxxxxxxxxxxxxx	xxx	xxx	xxxxxxxxxx	xxxxxxxxx/xxxxxxxxx	xxx	xxxxxxxxxx
		xxxxxxxx/	xxxxxxxx	xxxxxxxxxxxxxxxxxxxx						x
		xxxxxxxx		xxxxxxxxxxxxxxxxxxxx						
		xxxxxxxx		xxxxxxxxxxxxxxxxxxxx						

^a Adverse events coded with MedDRA Coding Dictionary Version xxx.

Cohort 1 = 100 μ g/5mCi IV; Cohort 2 = 100 μ g/10mCi IV; Cohort 3 = 200 μ g/5mCi IV and SC.

STATKING Clinical Services (DD-MMM-YYYY)

Source Program: xxxxxxx.sas

Page x of y

Data Listing 9. Subject Laboratory Profiles - Hematology Data Listing
Navidea Biopharmaceuticals - Study No. NAV3-24
Safety Population (N=xxx)

Cohort	Subject No.	Visit	Sample Date/ Time	Parameter (Units)	Result	Normal Range		Clin. Sig?
						Lab Low	Lab High	
xxxxxx	xxxx	xxxxxxxx	xxxxxxxx xx:xx	xxxxxxxxxxxx (xxx)	xxx	xxx	xxx	xxx
				xxxxxxxxxxxx (xxx)	xxx	xxx	xxx	xxx
				xxxxxxxxxxxx (xxx)	xxx	xxx	xxx	xxx
				xxxxxxxxxxxx (xxx)	xxx	xxx	xxx	xxx
				xxxxxxxxxxxx (xxx)	xxx	xxx	xxx	xxx
				xxxxxxxxxxxx (xxx)	xxx	xxx	xxx	xxx

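### SAP 5.0 starts the treatment-emergent period on the calendar day of first dosing, the protocol at the injection time, so AEs recorded on Day 1 before the first injection would be tabulated as treatment-emergent

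*SAP*

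**What the plan says.** The two definitions differ in one element:

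- SAP 5.0: a TEAE is "an adverse event whose start date is on or after the first study drug administration date".
- Protocol 9.5.4: a TEAE is "an adverse event whose start date is on or after the Tc 99m tilmanocept injection date and time".

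Both treat an AE as treatment-emergent when its start date or the dosing information is missing. Here too the protocol refers to the date and time of injection and the SAP to the date only. The SAP does not present this as an intended departure.

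The documents also differ on which events before the injection become AEs:

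- Protocol 8.6.1.1 cuts by calendar day: "all untoward medical occurrences beginning on the day of Visit 2 Baseline (Day 1) through the Follow-up Phone Call are to be reported as AEs". Section 8.6.1.3 repeats the rule. Only events before that day go to medical history, and only if unrelated to a study procedure.
- SAP 5.0 cuts at the injection: "Events occurring prior to Tc 99m tilmanocept administration will be recorded in the subject's medical history unless determined to be related to the study procedure".

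Onset time is available. Protocol 8.6.1.3 requires the "date and time of onset" of each AE, and Data Listing 8 in SAP Appendix B has a column for "AE Start Date and Time".

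**The concern.** Protocol 7.2.1 and 7.4.1 schedule an AE assessment on Day 1 before the injection, so an event can be recorded as an AE on the dosing day while the subject is still undosed. In Cohorts 1 and 2, whose Day 1 injection is intravenous, a catheter is also placed beforehand (protocol 8.2), so a procedural event in that interval is plausible. A programmer following the SAP would flag such an event as treatment-emergent, although it began before any exposure.

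The SAP plans one pair of tables for all AEs (16 and 17) and another for TEAEs (18 and 19). Events before Day 1 become AEs only if they are procedure-related, apart from SAEs, which are reported from consent. The hours before the Day 1 injection are thus one of the few places where the two pairs should differ, and the date-only rule removes that difference. With cohorts of four to six, one subject is a large percentage.

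**Working it through.** **Inputs**

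- TEAE rules: SAP 5.0 (date of first administration) and protocol 9.5.4 (date and time of injection).
- Planned sizes: 4, 4 and up to 6, total up to 14 (protocol Table 1; SAP Table 1).
- Assumption for illustration: first injection at 10:00 on Day 1.

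**Step 1: apply both rules to four onset times**

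| Onset of AE | Protocol rule (date and time) | SAP rule (date only) |
|---|---|---|
| Day before Day 1, 09:00 | not a TEAE | not a TEAE |
| Day 1, 08:30 (before injection) | not a TEAE | TEAE |
| Day 1, 10:20 (after injection) | TEAE | TEAE |
| Day 2, 09:00 | TEAE | TEAE |

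The rules disagree only between the start of Day 1 and the first injection, and there the SAP can only add events.

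**Step 2: which events in that interval are AEs at all**

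| Type of Day 1 pre-injection event | Under the SAP medical-history sentence | Under protocol 8.6.1.1 and 8.6.1.3 |
|---|---|---|
| Procedure-related | AE, so flagged as a TEAE | AE, so flagged as a TEAE |
| Not procedure-related | medical history, so no flag | AE, so flagged as a TEAE |

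The affected set is the first row at least, and both rows at most.

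**Step 3: size for one affected subject**

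The percentage of subjects with at least one TEAE moves by 100 × 1/n if the subject has no other TEAE, and by zero otherwise.

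- Cohort of 4: 100 × 1/4 = 25.0 points.
- Cohort of 6: 100 × 1/6 = 16.7 points.
- Overall, 14 subjects: 100 × 1/14 = 7.1 points.

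The total number of TEAEs in Table 18 rises by one per misclassified event in either case.

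**Step 4: Cohort 3**

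Cohort 3 receives the SC injection on Day 1 and the IV injection on Day 7 ± 3. Its catheter placement follows the first injection, so an event from that placement is treatment-emergent under a first-injection rule with or without a time. The SAP specifies the first administration; protocol 9.5.4 does not say which of the two injections it means.

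**The case against.** The strongest reply is the SAP's own medical-history sentence, which stands directly before the TEAE definition. A reader might infer that the date-only rule turns every Day 1 pre-injection event into a TEAE. Under the SAP's text it does not: an event unrelated to the procedure goes to medical history and never reaches the TEAE tables. That limit stands as far as the SAP goes. It does not dispose of the point, because procedure-related events remain, and because sites record AEs under the protocol, whose calendar-day rule conflicts with the SAP sentence.

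A reader might also infer that catheter placement exposes all three cohorts. It applies to Cohorts 1 and 2 only, since Cohort 3 has an SC injection on Day 1.

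Nor should the primary result be thought at risk. The ADR endpoint rests on a causal link to the product, and protocol 9.2 counts ADRs following injection. Escalation under protocol 5.3 also runs on ADRs. Neither uses the TEAE flag.

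Finally, the TEAE tables are not causal counts. Table 19 reports relationship to drug and to procedure separately, and with about 14 subjects a reader could find a misclassified event in Data Listing 8. This limits the harm but does not make the tables follow the protocol.

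**Conclusion.** The inconsistency is real and minor. As written, the SAP would count as treatment-emergent any AE recorded on Day 1 before the first injection, contrary to protocol 9.5.4. This affects Tables 18 and 19 and the flag in Data Listing 8. The error over-counts TEAEs and cannot hide one.

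The shifts of 25.0, 16.7 and 7.1 points are effects per subject. They assume planned cohort sizes and an affected subject with no other TEAE. The documents give no expected frequency of such events, so the shifts do not predict what the tables will show.

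**What to change.** Make three edits to SAP 5.0:

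1. Define a TEAE as an AE whose onset date and time fall at or after the date and time of the **first** Tc 99m tilmanocept injection. Copying the protocol's wording would not be enough: it omits the word first and leaves the start of the period unclear for Cohort 3. Take the injection time from the data behind Data Listing 15. Data Listing 8 shows the most recent injection, which has no value for an AE before the first one.
2. State that an AE on the first-injection date with no onset time is treated as emergent. Neither document covers this case. The rule is an addition, in line with their existing convention for missing dates.
3. Reconcile the medical-history sentence with protocol 8.6.1.1 and 8.6.1.3, so that one rule decides which Day 1 pre-injection events are AEs.

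If the date-only rule is intended, the SAP should say so and justify the departure. The cost is a few sentences and one line of programming; onset and injection times are already collected.

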1.0 Synopsis of Study Design Procedures

This study will enroll up to fourteen (14) HIV (human immunodeficiency virus) - positive female or male subjects at least 18 years of age who have biopsy-confirmed Kaposi Sarcoma (KS).

The primary objective of this study is:

- To determine the safety of escalating doses of Tc 99m tilmanocept in HIV subjects with biopsy-confirmed KS

The secondary objectives of this study are:

- Concordance between clinical assessment/diagnosis and the localization of Tc 99m tilmanocept by planar and/or SPECT (single photon emission computed tomography) / CT (X-ray computed tomography) imaging in cutaneous and non-cutaneous sites of KS.
- Qualify and quantify Tc 99m tilmanocept localization intensity on imaging with CD206 locale and quantity by histology and immunohistochemistry (IHC) in biopsied KS lesions to determine optimal IV dose.
- Concordance of localization of Tc 99m tilmanocept via IV and SC routes of administration by planar and/or SPECT/CT imaging in cutaneous and non-cutaneous sites of KS.

The exploratory objective of this study is:

- Quantify HHV8 in biopsied KS lesions by real-time polymerase chain reaction (qPCR)

General safety will be evaluated by examining the incidence of adverse events (AEs) and changes over time in laboratory tests, vital signs, ECGs (electrocardiogram) and physical examination findings.

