(mean, standard deviation, minimum, median, maximum, range, n) on the raw values as well as their changes from pre-injection on Day 1 (and Day 7 [\pm 3] for Cohort 3) will be presented by dose group and overall. Time points included in this analysis are Day 1 (and Day 7 [\pm 3] for Cohort 3) within 30 minutes pre-injection and within 30 minutes post-Injection. If repeat vital signs are taken at a given time point, then the last measurement will be used for the analysis tables. A shift table will be created showing shifts Abnormal/Abnormal, Abnormal/Normal, Normal/Abnormal, Normal/Normal from pre-injection to post-injection of Tc 99m tilmanocept. This analysis will be performed by dose group and overall.

All vital signs will be listed, including those not presented in the analysis tables.

Physical Exams

A complete physical exam will be performed during screening. A data listing of the physical exam results will be created as shown in [Appendix B](#).

Concomitant Medications

All concomitant medications will be coded with WHO Drug Dictionary (Uppsala Monitoring Centre) version March 2017 or later. A data listing will be constructed with Preferred Term, Verbatim Term, ATC Level 1 Code, and ATC Level 4 Code. A summary table will be provided to show the counts and percentages of subjects taken medications by ATC Level 4 Code and Preferred Term by dose group and overall.

Clinical Laboratory Parameters

Changes in hematology, clinical serum chemistry and urinalysis between screening (i.e., baseline) and the post-injection time point will be calculated, and descriptive statistics will be calculated on the raw and change from baseline values by dose group and overall. A copy of the normal laboratory values for all laboratories utilized for this study will be submitted to the Sponsor (or designee) prior to initiation of the study. A shift table will be created showing shifts Abnormal/Abnormal, Abnormal/Normal, Normal/Abnormal, Normal/Normal from screening baseline to post-injection of Tc 99m tilmanocept. This analysis will be performed by dose group and overall.

ECG

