		Normal/Post Normal	Abnormal/Post Normal	Normal/Post Abnormal	Abnormal/Post Abnormal
Cohort 1 IV	xxxxxxxxxx (xxx)	xxx	xxx	xxx	xxx
	xxxxxxxxxx (xxx)	xxx	xxx	xxx	xxx
	xxxxxxxxxx (xxx)	xxx	xxx	xxx	xxx
Cohort 2 IV	xxxxxxxxxx (xxx)	xxx	xxx	xxx	xxx
	xxxxxxxxxx (xxx)	xxx	xxx	xxx	xxx
	xxxxxxxxxx (xxx)	xxx	xxx	xxx	xxx
Cohort 3 IV	xxxxxxxxxx (xxx)	xxx	xxx	xxx	xxx
	xxxxxxxxxx (xxx)	xxx	xxx	xxx	xxx
	xxxxxxxxxx (xxx)	xxx	xxx	xxx	xxx
Cohort 3 SC	xxxxxxxxxx (xxx)	xxx	xxx	xxx	xxx
	xxxxxxxxxx (xxx)	xxx	xxx	xxx	xxx
	xxxxxxxxxx (xxx)	xxx	xxx	xxx	xxx
All IV Cohorts	xxxxxxxxxx (xxx)	xxx	xxx	xxx	xxx
	xxxxxxxxxx (xxx)	xxx	xxx	xxx	xxx
	xxxxxxxxxx (xxx)	xxx	xxx	xxx	xxx

Cohort 1 = 100µg/5mCi IV; Cohort 2 = 100µg/10mCi IV; Cohort 3 = 200µg/5mCi IV and SC.

STATKING Clinical Services (DD-MMM-YYYY)

Source Program: xxxxxxxx.sas

Table 24. Clinical Laboratory Parameters Summary Statistics
 Navidea Biopharmaceuticals - Study No. NAV3-24
 Safety Population (N=xxxx)

Group	Laboratory Panel/ Parameter (units)	Visit	Data Type ^a	Mean	Std Dev	n	Min	Max	Median
Cohort 1 IV	xxxxxxxxxxxxxx/ xxxxxxxxxx (xxx)	Screening (Baseline)	RAW	xxx	xxx	xxx	xxx	xxx	xxx
		Post-Injection	RAW CFB	xxx xxx	xxx xxx	xxx	xxx	xxx	xxx
Cohort 2 IV	xxxxxxxxxxxxxx/ xxxxxxxxxx (xxx)	Screening (Baseline)	RAW	xxx	xxx	xxx	xxx	xxx	xxx
		Post-Injection	RAW CFB	xxx xxx	xxx xxx	xxx	xxx	xxx	xxx
Cohort 3 IV	xxxxxxxxxxxxxx/ xxxxxxxxxx (xxx)	Screening (Baseline)	RAW	xxx	xxx	xxx	xxx	xxx	xxx
		Post-Injection	RAW CFB	xxx xxx	xxx xxx	xxx	xxx	xxx	xxx
Cohort 3 SC	xxxxxxxxxxxxxx/ xxxxxxxxxx (xxx)	Screening (Baseline)	RAW	xxx	xxx	xxx	xxx	xxx	xxx
		Post-Injection	RAW CFB	xxx xxx	xxx xxx	xxx	xxx	xxx	xxx
All IV Cohorts	xxxxxxxxxxxxxx/ xxxxxxxxxx (xxx)	Screening (Baseline)	RAW	xxx	xxx	xxx	xxx	xxx	xxx
		Post-Injection	RAW CFB	xxx xxx	xxx xxx	xxx	xxx	xxx	xxx

^a RAW = data recorded in database; CFB = change from baseline
 Cohort 1 = 100µg/5mCi IV; Cohort 2 = 100µg/10mCi IV; Cohort 3 = 200µg/5mCi IV and SC.
 STATKING Clinical Services (DD-MMM-YYYY)
 Source Program: xxxxxxx.sas

Table 25. Clinical Laboratory Parameters Shift Table
 Navidea Biopharmaceuticals - Study No. NAV3-24
 Safety Population (N=xxxx)

Group	Laboratory Panel/Parameter (units)	Baseline	Baseline	Baseline	Baseline
		Normal/Post Normal	Abnormal/Post Normal	Normal/Post Abnormal	Abnormal/Post Abnormal
Cohort 1 IV	xxxxxxxxxxxxxx/xxxxxxxxxx (xxx)	xxx	xxx	xxx	xxx
	xxxxxxxxxxxxxx/xxxxxxxxxx (xxx)	xxx	xxx	xxx	xxx
	xxxxxxxxxxxxxx/xxxxxxxxxx (xxx)	xxx	xxx	xxx	xxx

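### The laboratory shift table sorts values only as Normal or Abnormal, so it loses the direction of new abnormalities and hides worsening or a low-to-high swing in a subject already out of range at screening

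*SAP*

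**What the plan says.** SAP 1.0 makes laboratory change part of the general safety evaluation, which examines adverse events and "changes over time in laboratory tests, vital signs, ECGs (electrocardiogram) and physical examination findings".

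SAP 5.0 (Clinical Laboratory Parameters) plans two summaries. The first is quantitative: "Changes in hematology, clinical serum chemistry and urinalysis between screening (i.e., baseline) and the post-injection time point will be calculated". Raw values are summarized alongside these changes, per cohort and pooled. Its shell is "Table 24. Clinical Laboratory Parameters Summary Statistics", which gives mean, SD, n, minimum, maximum and median of raw values and of changes. The second is categorical: "A shift table will be created showing shifts Abnormal/Abnormal, Abnormal/Normal, Normal/Abnormal, Normal/Normal from screening baseline to post-injection". Its shell is "Table 25. Clinical Laboratory Parameters Shift Table", with four columns per parameter for Cohort 1 IV, Cohort 2 IV, Cohort 3 IV, Cohort 3 SC and all IV cohorts. Neither the text nor the shell gives direction or degree.

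Appendix B also has subject-level listings. "Data Listing 9. Subject Laboratory Profiles - Hematology Data Listing" shows the result, the lower and upper laboratory limits and a clinical-significance flag for each parameter and visit. Listing 10 (serum chemistry) has the same columns.

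Protocol 9.5.4 asks only for descriptive statistics of observed values and changes, so the shift table is an addition made in the SAP.

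**The concern.** A shift table is meant to show who crossed a normal limit, and which way. This one records only whether a value is in or out of range at each time point. For an analyte with a lower and an upper limit, two things are lost:

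- **Direction of a new abnormality.** Normal to low and normal to high share one cell. Protocol 1.3.1 shows why this can matter: it reports minimal, dose-related, reversible AST increases in rats, and AST is one of the analytes measured here. A new high AST and a new low AST would look the same in Table 25.
- **Change within abnormal.** A low platelet count that falls further, or a value that moves from below to above range, is tabulated as Abnormal/Abnormal, like a value that did not move.

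In a study whose primary objective is safety, a reader who scans Table 25 could take an Abnormal/Abnormal count to mean no change.

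**Working it through.** **1. The plan's own figure.** SAP 1.3 gives cohorts of 4, 4 and up to 6, and a maximum of 14. Check: 4 + 4 + 6 = 14, which agrees.

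**2. What the four cells merge.** With L, N and H for low, normal and high, there are 3 × 3 = 9 transitions from screening to post-injection:

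| SAP cell | Transitions it contains |
|---|---|
| Normal/Normal | N→N |
| Normal/Abnormal | N→L, N→H |
| Abnormal/Normal | L→N, H→N |
| Abnormal/Abnormal | L→L, L→H, H→L, H→H |

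This follows from the definition and needs no assumption. A 3×3 table would separate N→L from N→H and expose L→H and H→L. It would not separate low from lower, or high from higher, because those stay in L→L and H→H.

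**3. A hypothetical illustration.** One subject goes from 1.2 to 6.0 times the upper limit (change 4.8). Another goes from 1.2 to 1.3 (change 0.1). Both are Abnormal/Abnormal. In Table 24, if the first subject is in a cohort of 4 and the other three do not change, the mean change is 4.8 / 4 = 1.2, the median is 0 and the maximum is 4.8. Table 24 therefore shows the large change, but not whether that subject began inside or outside the range.

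**4. Can subjects start out of range?** Protocol 4.1 and 4.2 contain no laboratory threshold. The only related criterion is the general clinical-judgment exclusion. Abnormal screening values are therefore allowed. Neither document says how common they are.

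**5. Size, over an assumed rate p.** p is the proportion of subjects out of range at screening on a given parameter. Expected number affected = 14 × p. Chance of at least one in n subjects = 1 − (1 − p)^n, taking subjects as independent with a common p.

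| p (assumed) | Expected of 14 | n = 4 | n = 6 | n = 14 |
|---|---|---|---|---|
| 5% | 0.7 | 0.19 | 0.27 | 0.51 |
| 10% | 1.4 | 0.34 | 0.47 | 0.77 |
| 20% | 2.8 | 0.59 | 0.74 | 0.96 |
| 30% | 4.2 | 0.76 | 0.88 | 0.99 |
| 50% | 7.0 | 0.94 | 0.98 | >0.99 |

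**6. Size across the table.** Protocol Table 2 lists 10 hematology, 13 chemistry and 2 urinalysis parameters, 25 in all. At full enrolment there are 14 IV and 6 SC injections, 20 in all. That gives up to 25 × 20 = 500 entries before pooling. The expected number with an abnormal baseline, where the table cannot show worsening, is 500 × 0.05 = 25 to 500 × 0.50 = 250.

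**The case against.** The strongest reply is that Table 25 is one descriptive display among several and that nothing is decided on it.

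- Protocol 8.6.2.4 requires prompt review of every laboratory report. Changes that alter subject management are recorded as adverse events whatever the baseline category.
- Table 24 prints the minimum and maximum change per cohort and route. With 4 to 6 subjects, these are individual subjects' values.
- Listings 9 and 10 show each result beside its limits, and with at most 14 subjects they can be read line by line.
- The primary endpoint (Protocol 9.2) and dose escalation (Protocol 5.3) rest on adverse drug reactions, not on this table.

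All of this stands, and it keeps the point small. It does not remove it. The adverse event rule reaches only changes that alter management, Table 24 does not tie a change to the baseline category or the normal range, and the listings are not a summary. No planned table shows movement relative to the range by direction.

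A reader might infer more than the documents support, in three ways:

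- That an HIV-positive population with Kaposi sarcoma is likely to start abnormal. Neither document says so or gives a rate; they show only that abnormal values are allowed.
- That the table ignores the laboratory limits. SAP 5.0 refers to the laboratories' normal values just before it describes the shift table, so the Normal/Abnormal split presumably rests on them. What is missing is direction.
- That the urinalysis listing also carries limits. The columns of Listing 11 cannot be seen in the available text, so this can be confirmed only for Listings 9 and 10.

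**Conclusion.** The point holds as a minor weakness in a secondary safety table. The loss of direction, and the pooling of stable, worsening and swinging values in Abnormal/Abnormal, follow directly from the stated method. How many subjects are affected depends wholly on an assumed baseline abnormality rate: about 1 to 7 of 14 per parameter for rates of 5% to 50%. It would be wrong to conclude that laboratory deterioration would go unseen in this trial, because Table 24, Listings 9 and 10 and adverse event recording can still reveal large or management-changing shifts. The primary endpoint is unaffected.

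**What to change.** In SAP 5.0 and the Table 25 shell:

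1. Replace the four columns with Low/Normal/High at screening by Low/Normal/High post-injection (nine cells), using the laboratory limits shown in Listings 9 and 10. Confirm that the same limits are held for the urinalysis parameters.
2. For subjects outside range at screening, add the number whose post-injection value moved further beyond the same limit, and show the size of each change. The 3×3 table alone leaves low-to-lower and high-to-higher hidden. The size is needed because screening may be up to 30 days before injection, and a bare count would treat trivial variation as worsening.

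The cost is table programming and a revised shell, with no new data. The table becomes wider and sparser, with 4 to 6 subjects per cohort row. The vital-sign and ECG shift tables use the same two categories, but the same change does not carry over directly: Listing 14 shows a normal flag without limits, and the ECG shift rests on an overall assessment.
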